**APPENDIX 4. AESI AND OTHER AES CRITERIA**

AESI	Search Criteria
Anaphylactic reactions	Narrow SMQ for “anaphylactic reaction”
Systemic hypersensitivity reactions	Narrow SMQ for “hypersensitivity” Note: manual adjudication of relevant PTs will be required by the study medical monitor, before database lock
Helminthic infections	Include the following HLTs 1. HLT = Cestode infections 2. HLT = Helminthic infections NEC 3. HLT = Nematode infections 4. HLT = Trematode infections
Any severe type of conjunctivitis or blepharitis	Broad CMQ Conjunctivitis PTs Conjunctivitis Conjunctivitis allergic Conjunctivitis bacterial Conjunctivitis viral Atopic keratoconjunctivitis Blepharitis Dry eye

	
Eye irritation                  Eye pruritus                  Lacrimation increased                  Eye discharge                  Foreign body sensation in eyes                  Photophobia                  Ocular hyperaemia                  Conjunctival hyperaemia                  Xerophthalmia,
 
and
 
PTs:                  Bacterial blepharitis                  Blepharitis allergic
 
AND
 
Serious AE= “Yes” OR Severity= “severe”

Keratitis	Narrow SMQ for “corneal disorders”
Clinically symptomatic eosinophilia	
HLT = Eosinophilic disorders
 
OR
 
PT = Eosinophil count increased

	Note: manual adjudication of relevant PTs will be required by the study medical monitor, before database lock.
Other AEs	Search Criteria
Skin Infections	SOC = (' Infections and infestations ', ' Skin and subcutaneous tissue disorders ')
Herpes Infections	HLT = Herpes viral infections
Injection Site Reactions	HLT = Injection Site Reactions

The search criteria are meant to assist the process of identification of TEAE of Special Interest/TEAE Syndrome. However, since these criteria might not be exhaustive in some cases or may not be specific in other cases. Hence an additional blinded review of all PTs in the database may be performed by the Medical monitor, based on medical judgement, to identify any TEAE of Special Interest/TEAE Syndrome that might have been missed by the criteria or to identify any TEAE may be inaccurately assigned as AESI by the algorithmic search

**APPENDIX 5. PCSV CRITERIA**

Criteria for Treatment-Emergent Potentially Clinical Significant Value for Pediatric Patients ( $\geq$  6months to  $<$ 6 years old)

Age range	Parameter	TE PCSV	Comments
	Vital Signs		Ref. : Kidney Disease Outcomes Quality Initiatives (KDOQI) Guideline 13; 1996; The fourth report on the diagnosis, evaluation, and treatment of high blood pressure in children and adolescents, Pediatrics 2004; Bowman E & Fraser S Neonatal Handbook 2012; Mulberg AE et al. Pediatric Drug Development Concepts and applications. John Wiley & sons, Inc. 2009; Pediatric respiratory rates http://www.health.ny.gov/
6 months - $<$ 1 year	HR	$\leq$ 72 bpm and decrease from baseline $\geq$ 20 bpm $\geq$ 175 bpm and increase from baseline $\geq$ 20 bpm	

1- <3 years	HR	$\leq 63$ bpm and decrease from baseline $\geq 20$ bpm $\geq 140$ bpm and increase from baseline $\geq 20$ bpm	
3-<6 years	HR	$\leq 59$ bpm and decrease from baseline $\geq 20$ bpm $\geq 140$ bpm and increase from baseline $\geq 20$ bpm	
6 months -<1 year	SBP	$\leq 70$ mmHg and decrease from baseline $\geq 20$ mmHg $\geq 110$ mmHg and increase from baseline $\geq 20$ mmHg	
1 - <3 years	SBP	$\leq 70$ mmHg and decrease from baseline $\geq 20$ mmHg $\geq 116$ mmHg and increase from baseline $\geq 20$ mmHg	
3-<6 years	SBP	$\leq 70$ mmHg and decrease from baseline $\geq 20$ mmHg $\geq 121$ mmHg and increase from baseline $\geq 20$ mmHg	

6 months -< 1 year months	DBP	$\leq 34$ mmHg and decrease from baseline $\geq 10$ mmHg $\geq 72$ mmHg and increase from baseline $\geq 10$ mmHg	
1-<3 years	DBP	$\leq 34$ mmHg and decrease from baseline $\geq 10$ mmHg $\geq 77$ mmHg and increase from baseline $\geq 10$ mmHg	
3 - <6 years	DBP	$\leq 34$ mmHg and decrease from baseline $\geq 10$ mmHg $\geq 83$ mmHg and increase from baseline $\geq 10$ mmHg	
6 months - <6 years	Temperature	Rectal, ear or temporal artery: $\geq 102.2$ °F/39.0 °C Oral or pacifier: $> 102.2$ °F/39.0 °C Axillary or skin infrared: $> 102.2$ °F/39.0 °C	
6 months - <1 year months	Respiratory rate	$< 24$ per minute and $\geq 24$ per minute at baseline $> 40$ per minute and $\leq 40$ per minute at baseline	
1 - <6 years	Respiratory rate	$< 20$ per minute and $\geq 20$ per minute at baseline $> 34$ per minute and $\leq 34$ per minute at baseline	

6 months - <6 years	Weight	≥5 % weight loss from baseline	Based on identification of trends in the child's growth with a series of visits  WHO Multicentre Reference Study Group, 2006; Center for Disease Control. Growth chart 2007
	Clinical Chemistry		Ref Molleston JP et al. JPGN 2011; Moritz et al., Pediatrics 1999; Moritz et al., Pediatr Nephrol 2005 ; Sedlacek et al., Seminars in Dialysis 2006) Gong G et al. Clinical Biochemistry 2009; Masilamani et al. Arch Dis Children 2012; Mulberg AE et al. Pediatric Drug Development Concepts and applications. John Wiley & sons, Inc. 2009
6 months - <6 years	ALT	≥3 ULN and baseline <3 ULN	Based on normal ranges: 5 to 45 U/L (Females 6 months-<6 years) 5 to 49 U/L (Males 6 months- <6 years)
6 months - <6 years	AST	≥3 ULN and baseline <3 ULN	Based on normal ranges: 9 to 50 U/L (Females 6 months-<6 years) 9 to 60 U/L (Males 6 months-<6 years)
6 months - <6 years	Alkaline Phosphatase (ALP)	≥1.5 ULN and baseline < 1.5 ULN	Based on normal ranges: 70 to 350 U/L (6 months-<1 year) 125 to 320 U/L (≥1- ≤3 years) 150 to 370 U/L (≥4- <6 years)

6 months - <6 years	Total Bilirubin	$\geq 1.3$ ULN and baseline $< 1.3$ ULN	CF = mg x 1.7 = $\mu$ mol Based on normal ranges: $\leq 1$ mg/dL
6 months - <6 years	Conjugated Bilirubin	(Direct Bilirubin $> 35\%$ Total Bilirubin (TBILI) and TBILI $\geq 1.3$ ULN) and (Direct Bilirubin $\leq 35\%$ TBILI or TBILI $< 1.3$ ULN) at baseline	CF = mg x 1.7 = $\mu$ mol Based on normal range: 0 to 0.4 mg/dL
6 months- <6 years	ALT/AST and Total Bilirubin	((ALT $> 3$ ULN or AST $> 3$ ULN) and TBILI $> 2$ ULN) and ((ALT $\leq 3$ ULN and AST $\leq 3$ ULN) or TBILI $\leq 2$ ULN)) at baseline	
6 months - <6 years	CPK	$\geq 3$ ULN and $< 3$ ULN at baseline	
6 months - <1 year	Creatinine	$> 53$ $\mu$ mol/L or 0.6 mg/dL and $\leq 53$ $\mu$ mol/L or 0.6 mg/dL at baseline (Females 6 months- <1 year)  $> 62$ $\mu$ mol/L or 0.7 mg/dL and $\leq 62$ $\mu$ mol/L or 0.7 mg/dL at baseline (Males 6 months- <1 year)	CF = mg x 8.8 = $\mu$ mol
1- $\leq 3$ years	Creatinine	$> 62$ $\mu$ mol/L or 0.7 mg/dL and $\leq 62$ $\mu$ mol/L or 0.7 mg/dL at baseline	

4- <6 years	Creatinine	>71 $\mu\text{mol/L}$ or 0.8 mg/dL and $\leq 71$ $\mu\text{mol/L}$ or 0.8 mg/dL at baseline	
6 months - <6 years	Uric Acid	$\geq 8.0$ mg/dL or 476 $\mu\text{mol/L}$ and <8.0 mg/dL or 476 $\mu\text{mol/L}$ at baseline	CF = mg x 5.95 = $\mu\text{mol}$
6 months - <6 years	Blood Urea Nitrogen (BUN)	$\geq 6.4$ mmol/L or 18 mg/dl and <6.4 mmol/L or 18 mg/dl at baseline	
6 months - <6 years	Chloride	$\leq 80$ mmol/L or 80 mEq/L and >80 mmol/L or 80 mEq/L at baseline $\geq 115$ mmol/L or 115 mEq/L and <115 mmol/L or 115 mEq/L at baseline	CF = 1
6 months - <6 years	Sodium	$\leq 129$ mmol/L or 129 mEq/L and >129 mmol/L or 129 mEq/L at baseline $\geq 150$ mmol/L or 150 mEq/L and <150 mmol/L or 150 mEq/L at baseline	CF = 1
6months - $\leq 1$ year	Potassium	$\leq 3.5$ mmol/L or 3.5 mEq/L and >3.5 mmol/L or 3.5 mEq/L at baseline $\geq 6.1$ mmol/L or 6.1 mEq/L and <6.0 mmol/L or 6.0 mEq/L at baseline	
>1 - <6 years	Potassium	$\leq 3.5$ mmol/L or 3.5 mEq/L and >3.5 mmol/L or 3.5 mEq/L at baseline $\geq 5.5$ mmol/L or 5.5 mEq/L and <5.5 mmol/L or 5.5 mEq/L at baseline	

6 months - <6 years	Calcium total	$\leq 2.0$ mmol/L or 8.0 mg/dL and $> 2.0$ mmol/L or 8.0 mg/dL at baseline $\geq 2.9$ mmol/L or 11.6 mg/dL and $< 2.9$ mmol/L or 11.6 mg/dL at baseline	CF = mg x 0.025 = mmol
6 months - <6 years	Total Cholesterol	$> 6.20$ mmol/L or 240 mg/dL and $\leq 6.20$ mmol/L or 240 mg/dL at baseline	CF = g x 2.58 = mmol
6 months - <6 years	Triglycerides	$> 4.0$ mmol/L or 350 mg/dL and $\leq 4.0$ mmol/L or 350 mg/dL at baseline	After >12 hours of fast) CF = g x 1.14 = mmol
6 months - <6 years	Glucose	Hypoglycaemia: $< 2.7$ mmol/L and $\geq 2.7$ mmol/L at baseline (or $< 50$ mg/dL and $\geq 50$ mg/dL at baseline) Hyperglycaemia: $\geq 10$ mmol/L (unfasted) and $< 10$ mmol/L (unfasted) at baseline (or $\geq 180$ mg/dl and $< 180$ mg/dl at baseline); $\geq 7$ mmol/L (fasted) and $< 7$ mmol/L (fasted) at baseline (or $\geq 120$ mg/dL and $< 120$ mg/dL at baseline)	CF = g x 5.55 = mmol

	Hematology		Common Terminology Criteria for Adverse Events v3.0 (CTCAE), 2006 ; Division of Microbiology and Infections Diseases Pediatric Toxicity Tables, 2007 ; Division of AIDS Table for Grading the Severity of Adult and Pediatric Adverse Events, 2004; Mulberg AE et al. Pediatric Drug Development Concepts and applications. John Wiley & sons, Inc. 2009; Family Practice Notebook, LLC, 2012; Tietz NW et al. Clinical Guide to Laboratory Testing, 3 rd edition 1995
6 - 23 months	WBC	<4.0 GIGA/L or 4,000 /mm  and ≥ 4.0 GIGA/L or 4,000 /mm  at baseline >20.0 GIGA/L or 20,000 /mm  and ≤20.0 GIGA/L or 20,000 /mm  at baseline	
2 - <6 years	WBC	<3.0 GIGA/L or 3,000 /mm  and ≥ 3.0 GIGA/L or 3,000 /mm  at baseline >16.0 GIGA/L or 16,000 /mm  and ≤ 16.0 GIGA/L or 16,000 /mm  at baseline	
6 months- <1 year	Lymphocytes (ALC)	<2.0 GIGA/L or 2,000 /mm  and ≥ 2.0 GIGA/L or 2,000 /mm  at baseline >17.0 GIGA/L or 17,000/mm  and ≤17.0 GIGA/L or 17,000 /mm  at baseline	

≥1 - <6 years	Lymphocytes (ALC)	<1.0 GIGA/L or 1,000 /mm  and ≥ 1.0 GIGA/L or 1,000 /mm  at baseline >10.5 GIGA/L or 10,500/mm  and ≤10.5 GIGA/L or 10,500 /mm  at baseline	
6 months - <6 years	Absolute Neutrophil Count (ANC)	<1.2 GIGA/L or 1,200 /mm  and ≥ 1.2 GIGA/L or 1,200 /mm  at baseline (3-24 months)	
6 months - <6 years	Eosinophils	(>0.5 Giga/L and >ULN) and (≤0.5 Giga/L or ≤ ULN at baseline)	
6 - 23 months	Hemoglobin	< 1.40 mmol/L or 9.0 g/dL and ≥ 1.40 mmol/L or 9.0 g/dL at baseline or any decrease ≥ 0.31 mmol/L or 2 g/dL	
2 - <6 years	Hemoglobin	< 1.55 mmol/L or 10.0 g/dL and ≥ 1.55 mmol/L or 10.0 g/dL at baseline or any decrease ≥ 0.31 mmol/L or 2 g/dL	
6 - 23 months	Hematocrit	< 0.29 l/l or 29 % and ≥ 0.29 l/l or 29 % at baseline > 0.42 l/l or 42 % and ≤0.42 l/l or 42 % at baseline	
2 - <6 years	Hematocrit	< 0.32 l/l or 32 % and ≥ 0.32 l/l or 32 % at baseline > 0.47 l/l or 47 % and ≤ 0.47 l/l or 47 % at baseline	

6 months - <6 years	Platelets	<100 GIGA/L or 100,000 /mm  and ≥ 100 GIGA/L or 100,000 /mm  at baseline > 700 GIGA/L or 700,000 /mm  and ≤700 GIGA/L or 700,000 /mm  at baseline	
	ECG parameters		Ref. : Rijnbeek P.R. et al., Eur Heart J 2001; Davignon A. et al., Ped Cardiol 1979/1980; Semizel E.et al., Cardiol Young 2008; Mulberg AE et al. Pediatric Drug Development Concepts and applications. John Wiley & sons, Inc. 2009
6 - 23 months	PR	≥140 ms and <140 ms at baseline	
2 - <6 years	PR	≥160 ms and <160 ms at baseline	
6 - 23 months	QRS	≥85 ms and <85 ms at baseline	
2 - <6 years	QRS	≥95 ms and <95 ms at baseline	
6 months - <6 years	QTc	Absolute values (ms) Borderline: 431-450 ms and <431 ms at baseline Prolonged*: >450 to <500 ms and ≤450 ms at baseline Additional: ≥500 ms and <500 ms at baseline  Increase from baseline	To be applied to QTcF *QTc prolonged and DQTc>60 ms are the PCSA to be identified in individual subjects/patients listings.

		Borderline: Increase from baseline 30-60 ms Prolonged*: Increase from baseline >60 ms	
--	--	--	--

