4.2.1. Inclusion Criteria

A patient must meet the following criteria to be eligible for inclusion in the study:

1. Male or female ≥ 6 months to <6 years of age at the screening visit
2. Diagnosis of AD according to the American Academy of Dermatology consensus criteria at the screening visit
3. Patients with documented recent history (within 6 months before the screening visit) of inadequate response to topical AD medication(s)

NOTE:

- Patients who are unable to achieve and/or maintain remission and low disease activity (comparable to IGA 0=clear to 2=mild) despite treatment with a daily regimen of medium to higher potency TCS (\pm TCI as appropriate), applied for at least 28 days of use, or for the maximum duration recommended by the product prescribing information, whichever is shorter, will meet the definition of inadequate response for the purpose of this study.
- Patients with documented systemic treatment for AD in the past 6 months are also considered as inadequate responders to topical treatments and are potentially eligible for treatment with dupilumab after appropriate washout.
- Acceptable documentation includes contemporaneous chart notes that record topical medication prescription and treatment outcome, or investigator documentation based on communication with the patient's treating physician. If documentation is inadequate, potential patients may be offered a course of treatment with a daily regimen of TCS of medium potency (\pm TCI as appropriate*), applied for at least 28 days during the screening period or for the maximum duration recommended by the product prescribing information, whichever is shorter. Patients who demonstrate inadequate response, as defined above, or develop important side effects (eg, significant skin atrophy, systemic effects) during this period will still be eligible for inclusion in the study.

* TCIs are not permitted during the 2-week TCS standardization period. Investigators may substitute TCIs with low potency steroids on areas of skin on which TCIs are typically applied (eg, face, neck, intertriginous, and genital areas).

NOTE: The target population with respect to disease severity differs for part A (severe AD) and part B (moderate-to-severe AD). Therefore, disease severity criteria are specified separately for part A and part B in inclusion criterion 4 to 6 below:

4. IGA score at screening and baseline visits:
 - a. part A: IGA = 4
 - b. part B: IGA ≥ 3
5. EASI score at screening and baseline visits

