### 5.7.2. Analysis of Clinical Laboratory Measurements

Laboratory measurements include clinical chemistry, hematology and urinalysis results, and will be converted to standard international units and US conventional units. Summaries of laboratory variables will include:

- Descriptive statistics of laboratory result and change from baseline by visit

- The number (n) and percentage (%) of subjects with treatment emergent PCSVs. This summary will be provided based on all patients in the SAF as well as in the subgroup of SAF patients who did not meet the PCSV criterion at baseline.
- Shift tables based on baseline normal/abnormal and other tabular and graphical methods may be used to present the results for parameters of interest

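### Three rows of the SAP's laboratory PCSV table (neutrophils, glucose, infant potassium) disagree with themselves, so some descriptive safety flags are not uniquely defined

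*SAP*

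**What the plan says.** SAP Section 5.7 treats a PCSV as treatment-emergent when it newly arises, or becomes more severe than at baseline, during treatment or follow-up. It refers to Appendix 5 for the limits. SAP Section 5.7.2 promises counts and percentages of such PCSVs, both in the whole safety set and among patients who did not meet the criterion at baseline. It also says that laboratory results "will be converted to standard international units and US conventional units".

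The three rows in Appendix 5 read as follows.

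- **Neutrophils.** One row, "Absolute Neutrophil Count (ANC"), has 6 months to <6 years in its age column. Its only criterion is below 1.2 GIGA/L with a baseline of at least 1.2, closing with "at baseline (3-24 months".
- **Glucose.** The low limit is 2.7 mmol/L, paired with 50 mg/dL. The high unfasted limit is 10 mmol/L, paired with 180 mg/dL. The high fasted limit is 7 mmol/L, paired with 120 mg/dL ("mg/dL and $< 120$ mg/dL at baseline" for the baseline half). The comments column gives the factor: "CF = g x 5.55 = mmol".
- **Potassium, 6 months to 1 year.** The high side reads "6.1 mEq/L and <6.0 mmol/L or 6.0 mEq/L at baseline", where the first figure is the post-baseline limit. The row for >1 to <6 years uses 5.5 in both halves.

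**The concern.** Appendix 5 is what a programmer codes from. Each of these rows can be coded in more than one way, or gives a result that does not fit the definition in Section 5.7.

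For neutrophils the question is age scope. The age column covers every enrolled child, while the note stops at 24 months. For glucose, the flag near a limit depends on which unit is used, and the SAP does not say which unit governs. For infant potassium, the two halves of the row leave a gap. A child whose baseline lies in the gap is not a PCSV at baseline, yet can never be counted as developing one on the high side.

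At stake is whether the treatment-emergent PCSV counts are fixed in advance for these three analytes.

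**Working it through.** **Neutrophils (no arithmetic on the cut-off).** Eligibility is "Male or female ≥ 6 months to <6 years of age at the screening visit" (Protocol Section 4.2.1), which is months 6 to 72.

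- By the age column, all enrolled ages are tested against 1.2 GIGA/L.
- By the note, only months 6 to 24 are tested: 18 of 66 eligible months, or 27% of the age span. Older children then have no neutrophil criterion.
- The note starts at 3 months, below the minimum enrolment age.
- In the same table, WBC, haemoglobin and haematocrit each have separate rows for 6–23 months and 2 to <6 years. Neutrophils do not.

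There is one cut-off. The conflict is about who it applies to.

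**Glucose.** Convert with the row's own factor: mmol/L = (mg/dL ÷ 100) × 5.55.

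| Limit | Calculation | Result | Printed | Difference |
|---|---|---|---|---|
| High, unfasted, 180 mg/dL | 1.80 × 5.55 | 9.99 | 10 | −0.1% |
| High, fasted, 120 mg/dL | 1.20 × 5.55 | 6.66 | 7 | −4.9% |
| Low, 50 mg/dL | 0.50 × 5.55 | 2.775 | 2.7 | +2.8% |

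In reverse, 7 ÷ 5.55 × 100 = 126.1 mg/dL and 2.7 ÷ 5.55 × 100 = 48.65 mg/dL.

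Other pairs in the table, converted with their printed factors, agree within 1%:

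- uric acid: 80 mg/L × 5.95 = 476 (printed 476)
- calcium: 80 and 116 mg/L × 0.025 = 2.00 and 2.90 (2.0 and 2.9)
- cholesterol: 2.40 g/L × 2.58 = 6.19 (6.20)
- triglycerides: 3.50 g/L × 1.14 = 3.99 (4.0)
- creatinine: 6, 7 and 8 mg/L × 8.8 = 52.8, 61.6 and 70.4 (53, 62 and 71)

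The two discrepant glucose pairs are therefore not explained by the table's usual rounding.

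Effect on flags, with a baseline that meets neither version of the limit:

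- Fasted 125 mg/dL is 6.94 mmol/L: flagged in US units, not in SI. The window is 6.66 to <7.0 mmol/L.
- Any sample at 49 mg/dL is 2.72 mmol/L: flagged low in US units, not in SI. The window is 2.7 to <2.775 mmol/L.

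A baseline inside a window reverses the effect. A fasted baseline of 125 mg/dL rising to 127 mg/dL (7.05 mmol/L) is flagged in SI only, because in US units the baseline already meets the limit.

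**Infant potassium, high side (mmol/L).**

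| Baseline → post-baseline | As printed | 6.1 in both halves | 6.0 in both halves |
|---|---|---|---|
| 5.9 → 6.1 | flag | flag | flag |
| 6.0 → 6.5 | no flag | flag | no flag |
| 6.05 → 6.1 | no flag | flag | no flag |
| 6.1 → 6.5 | no flag | no flag | no flag |

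Under the printed row, a baseline of 6.0 or 6.05 is not a PCSV, since it is below 6.1. The later value is one, so by Section 5.7 it has newly arisen, yet the row does not flag it. Either single cut removes the inconsistency: with 6.1 the rise is flagged, and with 6.0 the baseline is itself a PCSV.

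**The case against.** The case for leaving this alone is that it is proofreading with little reach. Much of that stands.

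- **Neutrophils.** The table title and the age column both say 6 months to <6 years, and a note starting at 3 months looks like a leftover. The natural reading is one limit for all ages. A further limit for older children may also have been lost when the table was read from PDF; that cannot be excluded, but the printed label and note would still conflict. A reader might infer that neutropenia in older children would go unnoticed. The documents do not support that. Protocol Section 9.5.3.2 provides listings that flag out-of-range values, SAP Section 5.7.2 gives by-visit summaries, and Protocol Sections 5.4.2.1 and 5.4.2.2 set neutrophil limits for stopping or suspending dosing. A reader might also take the 48 of 66 months beyond age 2 (73%) as the share of patients affected. It is a share of the age span; the documents give no age distribution.
- **Glucose.** The fasted limit matters only for samples classed as fasted, and neither the schedule of events nor the laboratory sections require fasting. Converting results to both unit systems does not mean PCSVs are derived twice; a single derivation gives each result one flag. What remains is that the unit for that derivation is not stated. The low-glucose mismatch does not depend on fasting.
- **Potassium.** It would be wrong to say that a child with a baseline of 6.0 to <6.1 can never be flagged. The low-side limit of 3.5 still applies; only the high side is lost. Section 5.7 already states the general intent, but the row does not implement it.

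**Conclusion.** The point holds as a minor one. Three rows of Appendix 5 are inconsistent as printed, and each can change a flag.

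- Neutrophils: an ambiguity of age scope for children over 24 months, with a single cut-off.
- Glucose: disagreement between units over 6.66 to <7.0 mmol/L (fasted samples only) and over 2.7 to <2.775 mmol/L (any sample).
- Potassium: a 0.1 mmol/L gap on the high side, in children up to 1 year. If results are reported to one decimal, which is an assumption, only a baseline of exactly 6.0 is affected.

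The consequence is confined to descriptive PCSV counts. Efficacy endpoints, alpha and power are untouched. How many patients would change status cannot be worked out from the documents. The conclusion rests on the table as read from PDF and on the table's own conversion factors.

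**What to change.** Make three edits to Appendix 5 before the PCSV tables are programmed.

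1. Reconcile the neutrophil row's age column with its note, so that it is explicit which criterion, if any, applies to children over 24 months.
2. Make the fasted and low glucose pairs agree under the row's own factor, or state in Section 5.7.2 which unit governs PCSV flags. If the fasted limit is kept, say how a sample is classed as fasted.
3. Use one potassium cut in the baseline and post-baseline halves of the infant high-side criterion.

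The values are the sponsor's choice; the rows only need to agree with themselves. The cost is a short edit to one appendix table, with no change to data collection or to any other analysis.
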